#### 7.4.3 Subgroup Analyses

Subgroup analyses described in this section including figures will be performed for each of the efficacy endpoints, unless otherwise specified, for the subgroups in the FAS specified below:

- APOE e4 status
  - o e4 Carrier
  - Non-e4 carrier
- AD diagnosis
  - o Mild Cognitive Impairment (MCI) due to Alzheimer's disease
  - o Mild Dementia due to Alzheimer's disease
- Age group
  - $\circ$  < 65 years
  - $\circ \geq 65 < 75 \text{ years}$
  - $\circ$   $\geq$  75 years
- Sex
  - o Female
  - o Male

Subgroup analyses will be performed using the pMMRM model described in Section 7.4.1.1 by fitting the pMMRM model separately and respectively for each subgroup described above.

Subgroup analyses will also be performed using the MMRM model described in Section 7.4.1.2 by fitting the MMRM model separately and respectively for each subgroup described above.

If the pMMRM or MMRM model has convergence issue for a subgroup analysis, then only descriptive summaries will be provided for that subgroup.

<sup>a For both primary and supportive estimands.

same method as in Section 7.4.1.1

same model as in Section 7.4.1.2

Protocol No. AL002-2 Last Revision Date: 12 Aug 2025

Results will be reported for each subgroup separately and respectively.

LSMs line plots over time by treatment group will be displayed only for the primary efficacy endpoint and only for subgroups of APOE e4 status and AD diagnosis.

A forest plot of LSM difference at Week 96 and 90% CIs from MMRM will be drawn for all subgroups. In the same plot, the point estimates of the LSM difference at Week 96 and the proportional treatment effect from pMMRM will be displayed side by side.

## 7.5 Safety Analyses

Unless otherwise specified, all safety data will be summarized by treatment group, AL002 40 and 60 mg/kg combined group, and total AL002 group, primarily for the Non-e4/e4 Set. Some safety data may be summarized for the ATS.

Treatment period and analysis visit window definitions are described in Section 7.1.1.2.2.

In the case of multiple values in an analysis visit window and a single value may be required for each analysis visit window (e.g., CFB by visit usually requires a single value), data will be selected for analysis as described in Section 7.1.3.2, unless otherwise specified.

#### 7.5.2 Adverse Events

AE related terms such as TEAE, SAE, and AESI are defined in Section 6.3.2. A summary of AEs will present the number and percentage of participants who experienced at least 1 TEAE for the following events:

- TEAE (total and by maximum severity),
- Treatment-related TEAE (total and by maximum severity),
- TEAE leading to early study drug discontinuation,
- TEAE leading to study drug interruption,
- Treatment-emergent SAE,
- Treatment-related treatment-emergent SAE,
- Treatment-emergent AESI,
- Treatment-related treatment-emergent AESI,
- TEAE leading to death (i.e., outcome is fatal).

The number and percentage of participants who experienced at least 1 TEAE and the number and percentage of participants who experienced at least 1 treatment-related TEAE will be summarized by SOC, PT, and Severity. For other AEs described below, summaries will be provided by SOC and PT:

- TEAE (total and by severity),
- Treatment-related TEAE (total and by severity),
- TEAE leading to early study drug discontinuation,
- TEAE leading to study drug interruption,
- Treatment-emergent SAE,
- Treatment-related treatment-emergent SAE,
- Treatment-emergent AESI,
- Treatment-related treatment-emergent AESI,
- TEAE leading to death (i.e., outcome is fatal).

AEs will be summarized and listed first in alphabetic order of SOC and then by PT in descending order of total frequency within each SOC.

In addition to the above summary tables, TEAE, treatment-related TEAE, and treatment-emergent SAE will be summarized by PT only, in descending order of total frequency.

Additionally, the following summary tables will be provided for the ATS:

- The summary of AEs as described above,
- TEAE by PT in descending order of total frequency,

Protocol No. AL002-2 Last Revision Date: 12 Aug 2025

- TEAE leading to early study drug discontinuation by PT in descending order of total frequency,
- Treatment-emergent SAE by PT in descending order of total frequency.

In addition to the by-participant data listing of all AEs, separate by-participant data listings will also be provided for the following:

- TEAE leading to early study drug discontinuation,
- Treatment-emergent SAE,
- TEAE leading to death,
- Treatment-emergent AESI.

#### 7.5.2.1 Adverse Events Counting Rules

At the participant level, the following AE counting rules apply:

- A participant with more than one different AE in a particular SOC will be counted only once in the total of participants experiencing AEs in that particular SOC.
- A participant having experienced the same event, AE PT, more than once during the study will be counted only once in the number of participants with that event.
- If an event changes in intensity or in seriousness during the study, the participant will be counted only once with the worst grade and seriousness respectively.
- If the causal relationship to the study drug is assessed differently, it will be counted only once by considering the "worst" documented degree of relationship.

AEs reported with a relationship to study drug of related will be counted as treatment related. If the relationship is missing on the electronic CRF, this event will be included as 'related', and this will be noted.

#### **7.5.2.2** Deaths

SAEs resulting in death regardless of whether it is treatment-emergent or not will be summarized by SOC and PT, and will be listed including any appropriate information where available.

#### 7.5.3 Columbia Suicide Severity Rating Scale (C-SSRS)

For the C-SSRS, the number and percentage of participants with suicidal ideation, suicidal behavior, suicidal ideation or suicidal behavior, and non-suicidal self-injurious behavior as recorded on the C-SSRS scale, will be presented for each visit (refer to Table 7-2 for analysis visit window definition), and overall during the treatment period.

When summarizing the lifetime history of suicidal ideation, suicidal behavior, suicidal ideation or suicidal behavior, and non-suicidal self-injurious behavior, all related data recorded on the Screening/Baseline version will be included regardless of whether the assessment date is prior to, on, or after Study Day 1.

When summarizing the baseline (past 6 months for suicidal ideation, or past 2 years for suicidal behavior and non-suicidal self-injurious behavior), only related data recorded on the Screening/Baseline version prior to or on Study Day 1 will be included.

Protocol No. AL002-2 Last Revision Date: 12 Aug 2025

Only data recorded on the Since Last Visit version after Study Day 1 will be included in the treatment period.

A shift table from baseline (past 6 months for suicidal ideation, or past 2 years for suicidal behavior) to each post-baseline visit and to overall during the treatment period will be provided for suicidal ideation, suicidal behavior, and suicidal ideation or suicidal behavior. For overall, the response with the most severe suicidal ideation and suicidal behavior will be selected for a participant.

All C-SSRS data will be listed.

### 7.5.4 Laboratory Data

Laboratory data in summary tables and by-participant data listings will be presented in the International System of Units (SI units; Système International d'Unités).

When values are below or above a limit of quantitation, they will be listed as such, and the closest imputed value will be used for calculating summary statistics as specified in Section 7.1.4.

## 7.5.4.1 Numeric and Categorical Laboratory Results

For laboratory parameters that are continuous in nature, their laboratory data will be presented descriptively for each visit (refer to Table 7-3 and Table 7-4 for analysis visit window definition); the actual values and CFB will be summarized.

In addition, laboratory data will be summarized with shift tables from baseline to each post-baseline visit and overall during the post-baseline period, which include all post-baseline data, by laboratory test, where applicable. Each participant's hematology, chemistry, urinalysis, and coagulation non-missing numeric values will be flagged as "low", "normal", or "high" relative to the normal ranges of the central laboratory, when applicable. Each participant's urinalysis non-missing categorical values will be flagged as "positive" (or "present") or "negative" (or "absent"), when applicable. For each post-baseline visit shift summary for a given laboratory test, participants who had at least one post-baseline value at that visit and a baseline value will be included. For overall, participants will be categorized according to the most severe post-baseline category for a given laboratory test.

Local laboratory data will not be summarized or listed.

All laboratory data along with the normal ranges when applicable will be listed.

## 7.5.4.2 Toxicity Grades for Laboratory Results

Laboratory results will be assigned toxicity grades by the central laboratory based on the Common Toxicity Criteria for AEs (CTCAE) V5.0, when applicable. For a laboratory test, if the alert flag was normal and the toxicity grade was absent, then the toxicity grade will be assigned zero, and it is not considered as missing or unknown. Toxicity grades for laboratory results will be summarized with shift tables from baseline to each post-baseline visit and overall during the treatment period by laboratory test, for laboratory parameters that had at least one Grade 1 or above result at baseline or any time post-baseline. For overall, participants will be categorized according to the most severe post-baseline toxicity grade for a given laboratory test. Participants with a toxicity grade  $\geq 3$  will be marked in the by-participant data listing.

Protocol No. AL002-2 Last Revision Date: 12 Aug 2025

## 7.5.4.3 Potential Serious Hepatotoxicity

The number and percentage of participants meeting the criteria of potential serious hepatotoxicity (Section 6.3.4.2) will be summarized and will be listed.

## 7.5.5 Electrocardiogram (ECG)

Actual results and CFB values for the average of triplicate 12-lead ECGs (i.e., heart rate (beats/min), RR Interval (msec), QRS Duration (msec), QTcF Interval (msec)) will be summarized descriptively for each visit (refer to Table 7-5 for analysis visit window definition) and separated by predose and post-infusion (refer to Section 7.1.4.2 for handling of predose, post-infusion and "Not Applicable") per each visit. In addition, shift tables from baseline to post-baseline in the Investigator's overall interpretation of the ECG as indicated on the ECG electronic CRF will be provided for each visit. The summary will be separated by measurement time point (predose and post-infusion) per visit. Selection of data in the event of multiple records in an analysis visit window is specified in Section 7.1.3.2, separately for measurement time point (predose, post-infusion, and not applicable).

For the QTcF parameter as collected on the ECG electronic CRF, the number and percentage of participants in each criterion below will be summarized separated by measurement time point (predose and post-infusion) per visit and overall during the treatment period. For overall, the record with the most severe finding will be selected for a participant.

- Of the absolute QTcF interval prolongation:
  - $\circ$  > 450 msec.
  - $\circ$  > 480 msec,
  - $\circ$  > 500 msec.
- Of the CFBs in OTcF interval:
  - $\circ$  > 30 msec,
  - $\circ$  > 60 msec.

The number and percentage of participants in each criterion below (Table 7-23) will be summarized separated by measurement time point (predose and post-infusion) per visit and overall during the treatment period. For overall, the record with the most severe finding will be selected for a participant.

Table 7-23. ECG Parameter Criteria

ECG Parameter	Low Criteria	High Criteria
Heart Rate	< 50 beats/min	> 100 beats/min
RR Interval	< 600 msec	> 1200 msec
QRS Duration	< 60 msec	≥ 120 msec

All ECG data as collected on the ECG electronic CRF will be listed.

The same analyses described above will also be performed for the centrally read ECGs, when applicable.

Protocol No. AL002-2 Last Revision Date: 12 Aug 2025

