Grades 3 or 4 Grade 3: Prolonged (eg, not rapidly responsive to symptomatic medication and/or interruption of infusion); recurrence of symptoms following initial improvement; hospitalization indicated for clinical sequalae Grade 4: Life-threatening consequences; urgent intervention indicated	Stop infusion and increase monitoring of vital signs as medically indicated. Additional appropriate medical therapy may include but is not limited to IV fluids, IV steroids (eg, hydrocortisone 100-200 mg or corticosteroid equivalent), IV antihistamines, vasopressors, and antipyretics. Hospitalization may be indicated. Participants with signs or symptoms that may be consistent with cardiac etiology should be assessed by ECGs, cardiac enzymes (eg, creatinine-MB isoenzyme, troponins, brain natriuretic peptide) to rule out myocardial infarction, and echocardiogram should be performed unless cardiac failure is ruled out by preceding investigations. Participant is permanently discontinued from further trial treatment administration.	Any participant with a serious Grade 3 or any Grade 4 event will not be permitted to re-dose. Any subsequent redosing of nonserious Grade 3 events must be discussed and approved by the Medical Monitor.

CTCAE=Common Terminology Criteria for Adverse Events; ECG=electrocardiogram; IRR=Infusion-related reaction; IV=intravenous; MB=myocardial band; NSAIDs=non-steroidal anti-inflammatory drugs; po=orally.

AL002 Alector, Inc.

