## 7.1.4.2 Handling of Predose and Post-infusion

For vital signs and ECG data that collect measurement time points (predose, post-infusion, or "Not Applicable") on a study drug administration day, the following rules apply for assigning the measurement time points, when applicable.

- (1) For the assessments collected on Study Day 1:
  - The entries on the corresponding electronic CRF (predose, post-infusion) will be used.
    - o If the entry on the corresponding electronic CRF is "post-infusion", the assessment will be assigned the analysis visit "Day 1 Postdose". Measurement time points are not applicable for "Day 1 Postdose".
    - o If the entry on the corresponding electronic CRF is "predose", it will be considered as a candidate for baseline, and the baseline selection rules apply. Measurement time points are not applicable for baseline.
- (2) For the assessments collected at a post-Study-Day-1 scheduled visit, in which study drug is administered per the Schedules of Assessments in the protocol, the entries on the corresponding electronic CRF (predose, post-infusion) will be used, if the date of assessment is prior to or on the last dose date.
- (3) For the post-Study-Day-1 visits in which study drug is not administered per the Schedules of Assessments in the protocol, including Week 3 (vital signs only), Unscheduled, EFU, SFU, and ET, "Not Applicable" will be assigned as the measurement time point.
- (4) For the assessments collected after the last dose date, "Not Applicable" will be assigned as the measurement time point. And this takes precedence over the entries on the corresponding electronic CRF.
- (5) For the assessments collected prior to the first dose date, the measurement time points do not apply. And this takes precedence over the entries on the corresponding electronic CRF.

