## 7.5.6 Vital Signs

Vital signs data will be presented descriptively for each visit (refer to Table 7-7 and Table 7-8 for analysis visit window definition) and separated by predose and post-infusion (refer to Section 7.1.4.3 for handling of predose and post-infusion) per each visit; the actual values and CFB will be summarized. Selection of data in the event of multiple records in an analysis visit window is specified in Section 7.1.3.2, separately for measurement time point (predose, post-infusion, and not applicable).

A post-baseline vital signs value is considered treatment-emergent potentially clinically significant (PCS) if it meets both the observed value and the CFB criteria as listed in Table 7-24 during the treatment period. The number and percentage of participants with post-baseline treatment-emergent PCS vital signs will be summarized for each post-baseline visit and overall during the treatment period. The summary will be separated by measurement time point (predose, post-infusion, and not applicable) per visit or overall. For overall, the record with the most severe finding will be selected for a participant, separated by measurement time point (predose, post-infusion, and not applicable). Vital signs with measurement time point missing will only be included in the by-participant data listing.

All vital signs will be listed.

Table 7-24. Criteria for PCS Vital Signs

		Criteria a	
Parameter	Flag	Observed Value	CFB
Suming exertable blood masses (man He)	High	≥ 180	Increase of ≥ 20
Supine systolic blood pressure (mmHg)	Low	≤ 90	Decrease of $\geq 20$
Symina diastalia bla ad mussayus (mm.Ha)	High	≥ 105	Increase of $\geq 15$
Supine diastolic blood pressure (mmHg)	Low	≤ 50	Decrease of $\geq 15$
Suming mulas meta (hanta/min)	High	≥ 120	Increase of $\geq 15$
Supine pulse rate (beats/min)	Low	≤ 50	Decrease of $\geq 15$
Waight (Ira)	High	_	Increase of $\geq 7\%$
Weight (kg)	Low	_	Decrease of ≥ 7%

A post-baseline value is considered potentially clinically significant if it meets both the observed value and the CFB criteria.

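### On its natural reading, the SAP's ECG section tabulates only predose and post-infusion records, so ECGs labelled 'Not Applicable' within 90 days of the last dose reach only the listing and the worst-value outlier counts can be too low

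*SAP*

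**What the plan says.** **Labelling (SAP 7.1.4.2).** ECGs on Day 1 and at scheduled dosing visits up to the last dose date keep the predose or post-infusion entry from the eCRF. At visits after Day 1 where no drug is scheduled, "including Week 3 (vital signs only), Unscheduled, EFU, SFU, and ET", the time point is set to 'Not Applicable'. A further rule, which begins "For the assessments collected after the last dose date", sets the same label and overrides the eCRF entry.

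**ECG outputs (SAP 7.5.5).** Where a window holds several records, selection is done separately for three time points: predose, post-infusion and not applicable. The outputs name only two. The descriptive summary and the shift tables are split by predose and post-infusion at each visit. The QTcF counts (above 450, 480 and 500 msec; increases above 30 and 60 msec) and the heart rate, RR and QRS counts of Table 7-23 "will be summarized separated by measurement time point (predose and post-infusion) per visit and overall during the treatment period". For the overall row: "For overall, the record with the most severe finding will be selected for a participant". All ECG data on the eCRF are listed.

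**Comparator (SAP 7.5.6).** For potentially clinically significant (PCS) vital signs: "The summary will be separated by measurement time point (predose, post-infusion, and not applicable) per visit or overall".

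**Safety period.** SAP 7.5 refers to 7.1.1.2.2 for the treatment period. That section summarises safety data up to last dose plus 90 days and leaves later data to the listing.

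**The concern.** Three time points go into record selection in 7.5.5, and two come out in the tables. An ECG labelled 'Not Applicable' is assigned to an ordinary visit window, but the tables for that window have no place for it. The vital-signs PCS table is fed by the same labelling rule and does give it a place. SAP section 9, which lists changes from the protocol, records no decision to drop these ECGs, so this looks like an oversight.

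At stake are the counts a reader uses to judge cardiac safety, above all QTcF over 500 msec. A participant whose only such value was on an SFU ECG, an unscheduled ECG, or a scheduled ECG shortly after stopping drug would be shown as having none.

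**Working it through.** This is mainly a trace of rules, with day arithmetic. The SAP states no figure to reproduce.

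**Inputs**
- Dose n is given on Day 1 + 28(n − 1) (every 4 weeks, up to 25 doses).
- Scheduled post-baseline ECGs: Days 29, 85, 169, 337 and 561 (SAP Table 7-5 target days).
- ECG windows (SAP Table 7-5): Week 4 [2, 57], Week 12 [58, 127], Week 24 [128, 253], Week 48 [254, 449], Week 80 from Day 450.
- Upper bound for summaries: last dose day + 90.
- SFU: 8 weeks (56 days) after the final treatment-period visit, with a triplicate ECG marked in Protocol Table 9. It is not required for participants who enter the extension study (Protocol 3.3.4).
- Participants who stop drug are asked to stay on the visit schedule (Protocol 3.3.3).

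**SFU ECG, last dose at the final treatment visit**
- Last dose Day 337: SFU on 337 + 56 = Day 393. This is in the Week 48 window and before 337 + 90 = Day 427.
- Last dose Day 673: SFU on 673 + 56 = Day 729. This is in the Week 80 window and before 673 + 90 = Day 763.
- Both are labelled 'Not Applicable', so neither has a table cell.
- If the last dose was one visit earlier, the gap is 56 + 28 = 84 days, still inside. Two visits earlier it is 56 + 56 = 112 days, and the ECG is list-only under the separate 90-day rule.

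**Scheduled ECGs after drug is stopped, participant still attending (nominal days)**

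| Last dose number | Last dose day | Scheduled ECGs after last dose and within 90 days |
|---|---|---|
| 1 | 1 | Days 29 and 85 (limit Day 91) |
| 2, 3 | 29, 57 | Day 85 |
| 4, 5, 6 | 85, 113, 141 | Day 169 |
| 10, 11, 12 | 253, 281, 309 | Day 337 |
| 18, 19, 20 | 477, 505, 533 | Day 561 |
| any other | | none |

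Each of these is relabelled 'Not Applicable' and has no table cell. After a single dose, the Day 29 ECG is 28 days post-dose. That is the same interval as the predose ECG on Day 29 in a participant who continues, and that one is counted.

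**Unscheduled ECG between doses.** It is labelled 'Not Applicable', falls in a visit window, and has no table cell.

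In all these cases the two-time-point wording removes the ECG, not the 90-day limit.

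**Other overall rules in the SAP.** Laboratory overall shifts use all post-baseline data (7.5.4.1). The MRI tables for any occurrence of ARIA apply a worst-case rule (7.5.7). PCS vital signs report all three time points (7.5.6).

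**Scale of one missed participant (illustration).** Take the planned 328, less the 15 APOE e4 homozygotes and the 6 never dosed, and assume an equal split over arms. That gives (328 − 15 − 6)/4 ≈ 77 per arm and 307 × 3/4 ≈ 230 on AL002. One missed participant is then 1/77 ≈ 1.3% of an arm or 1/230 ≈ 0.43% of all AL002. How many would be missed is unknown.

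**The case against.** The strongest reply is that 'Not Applicable' is a label and not an exclusion. SAP 7.5.5 refers to the handling of 'Not Applicable' and selects such records per window, which would be pointless if they were never summarised. Day 1 Postdose also carries no time point, yet it is an analysis visit in Table 7-5. And the ECG sentence on the overall row does not repeat the split by time point, as the vital-signs sentence does, so a programmer could pool all records. This partly stands: the overall row is ambiguous. But the sentence before it ties the overall counts to the two named time points, and nothing says that the third is included. Day 1 Postdose has its own visit row, whereas the ECGs at issue fall in visits whose rows are split in two. If two programmers can reach different counts, the text needs settling under either reading.

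The second reply is that the signal is covered elsewhere. Clinically significant ECG findings are to be recorded as AEs (Protocol 7.4), and every ECG is listed. That limits the harm. But AE reporting rests on investigator judgement, and neither output gives a count of participants above a QTcF threshold.

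Four stronger readings are tempting and not supported:
- *That ECGs taken for infusion reactions are lost.* Protocol Appendix 3 says "Participants with signs or symptoms that may be consistent with cardiac etiology should be assessed by ECGs". An ECG done that day and recorded as post-infusion at the dosing visit keeps its label, even if that infusion is the last. Only one filed as unscheduled, or done on a later day, is relabelled.
- *That every unscheduled ECG is lost.* The rule covers visits after Day 1 only.
- *That vital signs keep three time points throughout.* The descriptive vital-signs summary also names only two. The contrast is with the PCS table.
- *That the arms are affected unequally, or that the dropped ECGs are the abnormal ones.* The loss depends on discontinuation and unscheduled visits, so imbalance is possible, but the documents give no data on either.

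**Conclusion.** The point holds as a gap in specification. On its natural reading, 7.5.5 leaves out of the shift tables and outlier counts ECGs that the SAP's own safety period includes. For the overall QTcF, heart rate, RR and QRS counts the direction is certain, because adding records to a worst-value rule cannot reduce the number of participants flagged. The size is unknown. It depends on how many participants stop drug and stay on study, how many have an SFU visit, and how many ECGs are filed as unscheduled.

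The conclusion assumes that the overall row is limited to the two named time points. If a programmer pools all records there, the overall counts are complete and only the by-visit shift and outlier tables lack these ECGs. The data are not lost in either case, since all ECGs are listed. The change is worth making before programming, because these counts are a main summary of ECG safety and the remedy is small.

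**What to change.** In SAP 7.5.5:
1. Add 'not applicable' as a third time point for the shift tables, the QTcF counts and the Table 7-23 counts, as the PCS vital-signs table in 7.5.6 does.
2. Define overall as the participant's worst post-baseline ECG up to last dose plus 90 days, regardless of measurement time point.

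The descriptive by-visit summary can stay at predose and post-infusion, as in 7.5.6.

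The cost is one more table category and its programming. No new data, visits or design changes are needed. Outlier counts may come out slightly higher.
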